Appendix 12 Standard Operation Procedures

Standard of Procedure Sweet Preference

Sweet Preference Task Setup

Script:

We will do the sweet preference task. We do this with our subjects to determine two things: whether they perceive things to be sweet and whether they are a “sweet liker”. You will be presented with 25 small cups of different solutions. I will hand you one at a time and you will swish each solution in your mouth for 5 seconds and then spit it out. After swishing the solution, you will then answer two questions on the computer about that solution you just tasted. You will then take a sip of water, swish and spit that out as well. You will then repeat this 25 times total. Remember not to swallow the solutions or the water.

ITEMS NEEDED:

1. Mini Cups
2. Tray
3. Permanent Marker
4. Pink Basin
5. SPT Solutions (5 vials of 5 solutions, 25 vials total)
6. Water

PROCEDURE:

Retrieve SPT Solutions from Nursing Station refrigerator

1. Take out 25 mini cups, label them 1-25
2. Lay out cups in 5 rows of 5 columns on the tray like below (with 1,6,11,16,21 facing closest to participant):

| | | | | | |
|---|----|----|----|----|---------------|
| 1 | 6 | 11 | 16 | 21 | ← A solutions |
| 2 | 7 | 12 | 17 | 22 | ← B solutions |
| 3 | 8 | 13 | 18 | 23 | ← C solutions |
| 4 | 9 | 14 | 19 | 24 | ← D solutions |
| 5 | 10 | 15 | 20 | 25 | ← E solutions |

PI Name: [name]., Ph.D., M.Sc.

3. Open the bag of "A" solutions and fill the first row of cups
4. Open the bag of "B" solutions and fill the second row of cups
5. Open the bag of "C" solutions and fill the third row of cups
6. Open the bag of "D" solutions and fill the fourth row of cups
7. Open the bag of "E" solutions and fill the fifth row of cups
8. Set up SPT Kiosk on computer for subject
9. Have subject swish Solution #1 for 5 seconds and spit into basin
10. Have subject complete SPT Kiosk for Trial #1 (two questions per trial)
11. Have subject swish water for 5 seconds and spit into basin
12. Repeat steps 9 through 11 for Solutions #2-25

Appendix 13

Snaith Hamilton Pleasure Scale (SHAPS)

Name:

Date:

Snaith Hamilton Pleasure Scale (SHAPS)

This questionnaire is designed to measure your ability to experience pleasure *in the last week*.

It is important to read each statement very *carefully*.

Mark *one* of the boxes [] to indicated how much you agree or disagree with each statement.

1. I would enjoy my favorite television or radio program:

Strongly disagree []

Disagree []

Agree []

Strongly agree []

2. I would enjoy being with my family or close friends:

Definitely Agree []

Agree []

Disagree []

Strongly disagree []

3. I would find pleasure in my hobbies and pastimes:

Strongly disagree []

PI Name: [name]., Ph.D., M.Sc.

Disagree []

Agree []

Strongly agree []

4. I would be able to enjoy my favorite meal:

Definitely Agree []

Agree []

Disagree []

Strongly disagree []

5. I would enjoy a warm bath or refreshing shower:

Definitely Agree []

Agree []

Disagree []

Strongly disagree []

6. I would find pleasure in the scent of flowers or the smell of a fresh sea breeze or freshly baked bread:

Strongly disagree []

Disagree []

Agree []

Strongly agree []

7. I would enjoy seeing other people's smiling faces:

Definitely Agree []

Agree []

Disagree []

Strongly disagree []

8. I would enjoy looking smart when I have made an effort with my appearance:

Strongly disagree []

Disagree []

Agree []

Strongly agree []

9. I would enjoy reading a book, magazine or newspaper:

Definitely Agree []

Agree []

PI Name: [name]., Ph.D., M.Sc.

Disagree []

Strongly disagree []

10. I would enjoy a cup of tea or coffee or my favorite drink:

Strongly disagree []

Disagree []

Agree []

Strongly agree []

11. I would find pleasure in small things, e.g. bright sunny day, a telephone call from a friend:

Strongly disagree []

Disagree []

Agree []

Strongly agree []

12. I would be able to enjoy a beautiful landscape or view:

Definitely Agree []

Agree []

Disagree []

Strongly disagree []

13. I would get pleasure from helping others:

Strongly disagree []

PI Name: [name]., Ph.D., M.Sc.

Disagree []

Agree []

Strongly agree []

14. I would feel pleasure when I receive praise from other people:

Definitely Agree []

Agree []

Disagree []

Strongly disagree []

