a) Sweet Preference Test. There is preclinical and clinical evidence linking the consumption of sweets to alcohol intake in both animals and humans ([name] et al., 2011). We will test the possible effects of individuals’ sweet preference characteristic on our study outcomes. Prior to administration, a visual examination of the sucrose solution for any particulate matter will be conducted by a clinician, proceeding only if no particulate matter is identified. Each subject will be instructed to sip, swish around his/her mouth and then spit out five different concentrations of a sweet solution (0.05, 0.10, 0.21, 0.42 and 0.83 M) each of which will be presented five times in a pseudorandom order for a total of 25 tastings. After each tasting, participants will rate the intensity and pleasurable-ness of each tasting using a 200-mm analog scale. Then, participants will rinse their mouths with distilled water before proceeding to the next solution. Subjects will be characterized as sweet-liker or sweet-disliker based upon their hedonic response to the various sucrose concentrations. To be categorized as a sweet-liker, a subject must rate the highest concentration of sucrose (0.83 M) as the most pleasurable. Sweet-dislikers could prefer any of the other four concentrations. As part of this test, subject will also fill out the Sweet Preference Questionnaire (see Appendix 7 and corresponding SOP for reference in Appendix 12).

b) Brief Addictive Behavior Social Density Assessment (BASDA). The BASDA is a self-reported assessment where participants self-report on their closest associates’ drinking behaviors (Bollinger et al., 2012). Participants are not asked to provide the names of their closest biological and non-biological associates. The goal is to explore the social milieu that usually surrounds the participant and to see if this information might help to predict craving behavior in our human laboratory setting.

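### The sweet preference script tells participants which label is being sought before they give the ratings that decide it; the same operating procedure also omits the clinician inspection set out in Section E, item 5(a)

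*Combined protocol and SAP*

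**What the plan says.** Section E, item 5(a) (Sweet Preference Test) describes five sucrose concentrations, each tasted five times, and states that "participants will rate the intensity and pleasurable-ness of each tasting using a 200-mm analog scale". It continues: "Subjects will be characterized as sweet-liker or sweet-disliker based upon their hedonic response". A sweet-liker is someone who rates the strongest solution, 0.83 M, as the most pleasurable; anyone who prefers another concentration is a sweet-disliker. The protocol intends to test whether this characteristic affects the study outcomes. Item 5 places the test among the characterizations done once, before study drug.

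Item 5(a) refers to Appendix 12 for the corresponding operating procedure. The script there precedes the procedure steps. It gives the reason for the task as "to determine two things: whether they perceive things to be sweet and whether they are a" sweet liker, and then explains the cups, swishing, rating and rinsing.

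On handling, item 5(a) says that before administration a "visual examination of the sucrose solution for any particulate matter will be conducted by a clinician", and that the test goes ahead only if none is found. Appendix 12 begins with "Retrieve SPT Solutions from Nursing Station refrigerator", goes on to labelling, laying out and filling cups and setting up the computer, and then reaches "Have subject swish Solution #1 for 5 seconds and spit into basin". No line mentions an inspection, a clinician or a stop condition.

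**The concern.** The label rests entirely on self-report, and the script names the category under test just before the self-report begins. A participant who already thinks of himself as someone who likes sweets, or does not, may rate the sweetest samples in line with that view. The label would then partly record self-image rather than response to taste. It is measured once, so no later measurement would correct it, and the protocol means to relate it to outcomes. The remaining script explains the task fully, so the disclosure serves no operational purpose.

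The second matter is one of consistency. The procedure that staff are pointed to does not carry a condition that the protocol body places on giving the solutions.

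**Working it through.** **1. Do the two texts describe the same test?** Item 5(a): 5 concentrations × 5 presentations = 25 tastings. Appendix 12: 5 vials of each of 5 solutions = 25 vials, poured into cups numbered 1 to 25. The counts agree, so the texts can be compared line by line.

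**2. Script against classification.**
- Told to the participant before tasting (Appendix 12): the task establishes whether the person is a sweet liker.
- Collected next (item 5(a)): intensity and pleasantness of each sample.
- Assigned from the pleasantness ratings (item 5(a)): sweet-liker or sweet-disliker.

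The disclosed category and the assigned category are the same. The script does not disclose the rule (0.83 M rated highest), does not say which cup holds which concentration, and does not suggest that either label is preferred.

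**3. What would disclosure have to do to change the label?** The rule compares concentrations within one person. If m_j is the mean pleasantness for concentration j, the person is a liker when m_0.83 is the largest of the five. Adding the same amount to every m_j leaves the ranking, and so the label, unchanged. Only a shift specific to some concentrations can move it.

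An illustration follows. All of its inputs are assumptions and none is in the documents: equal average liking of the five concentrations (100 mm), between-concentration SD 30 mm, between-repeat SD 20 mm, label taken from the mean of five repeats, 20,000 simulated participants.

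| Assumed shift in ratings | Share labelled liker |
|---|---|
| None | 20% (by symmetry 1/5) |
| +10 mm on all samples | 20% (simulated 19.7%; the difference is simulation noise) |
| +5 mm on 0.83 M only | 24% |
| +10 mm on 0.83 M only | 28% |
| +20 mm on 0.83 M only | 38% |

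This shows that a selective shift can move the label and a general one cannot. It does not estimate what the script does.

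**4. Does it reach the main comparison?** The test happens once, before drug, and each participant receives both drug and placebo. A wrong label does not alter that person's drug-placebo difference. Sweet preference is not a primary, secondary or tertiary outcome in Section D, and Section H names no analysis of it. Only the planned look at sweet preference and outcomes is exposed.

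**5. Inspection.** Item 5(a) has three elements: an examination, a clinician to do it, and a condition for proceeding. The Appendix 12 steps run unbroken from 1 to 12 and contain none of the three. Item 5(a) fixes the timing only as before administration, so the check could take place before the vials are taken from the refrigerator. The documents do not say.

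**The case against.** The strongest reply is that the influence of the script is conjecture. The participant hears a label but not the rule, and nothing in the text favours one answer. Participants would know the subject anyway: the recruitment text mentions tasting sweet solutions, the script's opening sentence names the task, and the Sweet Preference Questionnaire, whose order relative to the tasting is not stated, asks openly about craving sweets. All of this stands. It means that neutral wording hides the construct only in part and that no bias has been shown. It does not give a reason to name the category immediately before the ratings.

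On the inspection, a reader might infer that staff who follow Appendix 12 skip a safety check and give uninspected solutions. The documents do not support that. Item 5(a) remains a protocol requirement, assigns the check to a clinician, and cites the appendix only for reference. The check would be lost only if staff worked from the appendix alone and nobody applied item 5(a). What is shown is an operating procedure that is out of line with the protocol body.

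**Conclusion.** The point holds as a minor, avoidable disclosure. The script names the label that the participant's own ratings then decide, and the protocol plans to use that label. Influence is possible, because a rise confined to the sweetest samples would change the classification. That such a rise occurs is an assumption.

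No size can be given. A reader might want to state how far a liker-versus-disliker difference would be diluted. That needs a misclassification rate, the direction of the errors and the group sizes, and the documents supply none of these. The shares in the illustration depend wholly on assumed spreads and shifts. The primary drug-placebo contrast is not at risk.

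The missing inspection text is a separate matter of consistency between item 5(a) and Appendix 12. The two should be reconciled, with item 5(a) applying meanwhile.

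**What to change.** In the Appendix 12 script, replace the purpose sentence with a neutral one, for example: *You will taste 25 samples and rate how strong and how pleasant each one is.* The opening sentence that names the task can be made neutral in the same edit. Explain the purpose to the participant after the last rating. The remaining instructions can stay as they are.

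In the same revision, reconcile the Appendix 12 steps with the inspection and stop condition in Section E, item 5(a), so that both texts say the same about whether, when and by whom the check is done and recorded.

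The cost is about one page of revised procedure. It adds no visit, measurement or sample. The inspection is already assigned to a clinician in the protocol, so reconciling the texts creates no new task.
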